8.3 Study Period

The study period will start depending upon when the Omicron variant became established in Europe commencing from 1st December 2021.[8] The end of the study period will be the last available date of data collection for each contributing dataset.

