5. To estimate incidence rate ratios for venous and arterial thromboembolic events among patients with COVID-19 and different SARS-CoV-2 vaccine doses compared to the background population, using incidence rates estimated in objectives 1 to 3.

Study type: population-level cohort

Study population:

- 1) Pre-pandemic cohort to calculate background rates of venous and arterial thromboembolic events in the general population (year 2017-2019).
- 2) People with COVID-19 during the time when OMICRON was the dominant variant (coded or test positive). All participants are required to be visible in the data source since 1st January 2020 to have full records on infection and vaccination history.
- 3) People vaccinated against SARS-CoV-2 (+/- during the period when OMICRON was the dominant variant). All participants are required to be visible in the data source since 1st January 2020 to have full records on infection and vaccination history.

For all cohorts, individuals with recent VTE or ATE event (defined as having a diagnosis of VTE or ATE within 183 days prior to index date, with sensitivity analysis of using any time prior and 91-days as wash-out periods.) will be excluded.

	Phase II C3-001 – Study Protocol	
	Author(s): [name], [name]	Version: v3.1
		Dissemination level: public

Analysis:

Standardized incidence rate ratio (SIR) compared to the background population will be estimated using indirect standardization.

Cohorts will be stratified by prior COVID-19 infection occurrence and prior SARS-CoV-2 vaccination (COVID-19 and vaccine cohorts only), age, sex. All cohorts will additionally be stratified by whether patients are immunocompromised on the index date.

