7. RESEARCH QUESTION AND OBJECTIVES

The aim of the study is to contextualise the risk of venous and arterial thromboembolic events associated with COVID-19, during the Omicron period and SARS-CoV-2 vaccination. To do so, the research objectives are:

1. To estimate the background incidence rate of venous and arterial thromboembolic events among the general pre-pandemic population.
2. To estimate the incidence rate of venous and arterial thromboembolic events among patients with COVID-19 within 30-, 60-, and 90- and 180-days during the Omicron period, stratified by prior SARS-CoV-2 vaccination and prior infection status.
3. To estimate the incidence rate of venous and arterial thromboembolic events among patients with SARS-CoV-2 vaccination within 30-, 60-, 90- and 180-days, stratified by prior infection status.
4. To estimate a) the association between clinical risk factors, including prior SARS-CoV-2 vaccination, on the incidence rate of venous and arterial events among people with COVID-19 and b) the impact that thromboembolic events have on worsening severity of COVID-19 during the Omicron period.
5. To estimate incidence rate ratios for venous and arterial thromboembolic events among patients with COVID-19 and different SARS-CoV-2 vaccine doses compared to the background population, using incidence rates estimated in objectives 1 to 3.

Table X: Primary and secondary research questions and objective

A. Primary research question and objective

Objective:	
 1. To estimate the background incidence rate of venous and arterial thromboembolic events among the general pre-pandemic population. 2. To estimate the incidence rate of venous and arterial thromboembolic events among patients with COVID-19 within 30-, 60-, and 90- and 180-days during the Omicron period, stratified by prior SARS-CoV-2 vaccination and prior infection status.
-------------------	---

	Phase II C3-001 – Study Protocol	
	Author(s): [name], [name]	Version: v3.1
	Dissemination level: public	

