8.5 Study Population with inclusion and exclusion criteria

Five non-mutually exclusive study cohorts for the analyses will be defined:

- 1. General population cohort for pre-pandemic background rates** will have
 - Individuals will start contributing as of 1st January 2017, or when they have at least 365 days of data availability.
 - follow-up for this cohort will run up to 31 December 2019.
- 2. Persons tested positive for SARS-CoV-2 or with a clinical diagnosis of COVID-19 during the Omicron period** will
 - have either a positive test result for SARS-CoV-2 or a clinical diagnosis of COVID-19 on or after 1st December 2021 (with the index date being whichever date comes first if both occur)
 - have no positive test result for SARS-CoV-2 or clinical diagnosis of COVID-19 within 3 months prior to the index date.
 - have at least 365 days of data availability prior to index date
- 3. Persons hospitalised with COVID-19 during the Omicron period** will have
 - a hospitalisation on or after 1st December 2021 (with the index date the date of hospital admission),
 - a record of a clinical diagnosis of COVID-19 or a positive test result for SARS-CoV-2 in the period between 3 weeks prior to and up to 3 days following the index date.
 - have no diagnosis of COVID-19 or a positive test result for SARS-CoV-2 between 3 months and 3 weeks prior to index date.
 - have no COVID-19 hospitalisation within 3 weeks prior to the index date.
 - have at least 365 days of data availability prior to index date
- 4. Persons requiring intensive services during a hospitalisation with COVID-19 during the Omicron period** will have
 - intensive services initiated during a hospitalisation as described in cohort 3 (with the index date the date at which intensive services were initiated)
 - patients will have had a confirmatory diagnosis or test result of COVID-19 (both as defined above) within a time window from 3 weeks to their index date up to three days following their index date.
 - have at least 365 days of data availability prior to index date
- 5. Persons vaccinated against SARS-CoV2 infection**
 - a vaccination record identified by brand (with the index date the date of vaccination record)

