 - whether the vaccination record is 1st, 2nd, 3rd or 4th dose. A 21 day gap between two consecutive records of vaccine will be required to avoid repeated records of the same vaccine. The 21-days period was chosen based on the minimal recommended dosing schedule of the primary vaccine course in participated databases (Spain).
 - have at least 365 days of data availability prior to index date

Cohorts 2 to 5 will be stratified by prior COVID-19 infection status and for cohorts 2 to 4 also by prior SARS-CoV-2 vaccination status. All cohorts will additionally be stratified by whether patients are immunocompromised on the index date. People in each of the five cohorts will be required to have at least a year of observed history in the database prior to their index date. This is to ensure a sufficient time period to identify health conditions and medication use prior to individuals' index dates.

	Phase II C3-001 – Study Protocol	
	Author(s): [name], [name]	Version: v3.1
		Dissemination level: public

Table 3. Operational Definitions of Inclusion Criteria

Criterion	Details	Order of application	Assessment window	Care Setting ¹	Code Type	Diagnosis position ²	Applied to study populations:	Measurement characteristics/validation	Source for algorithm
Observation period of 365day prior entry (all 5 cohorts)	Study participants will be required to have 365 days prior history observed before contributing observation time	before	[-365,0]	n/a	n/a	n/a	All individuals within the selected databases	n/a	n/a
Covid-19 infection (cohort 2)	have either a positive test result for SARS-CoV-2 or a clinical diagnosis of COVID-19 on or after 1 st December 2021 (with the index date being whichever date comes first if both occur)	before	n/a	Primary care	SNOMED	n/a	All individuals within the selected databases	n/a	n/a
Covid-19 hospitalized (cohort 3)	a hospitalisation on or after 1 st December 2021 (with the index date the date of hospital admission), a record of a clinical diagnosis of COVID-19 or a positive test result for SARS-CoV-2 in the period between 3 weeks prior to and up to 3 days following the index date	before	[-21, 3]	Primary care, secondary care	SNOMED	n/a	All individuals within the selected databases	n/a	n/a

	Phase II C3-001 – Study Protocol	
	Author(s): [name], [name]	Version: v3.1
	Dissemination level: public	

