The included databases will vary in the data elements that they capture and in their current duration of follow-up. Depending on the dataset, not all study populations will be observed. For example, identifying the intensive services cohort will not be possible where inpatient hospital interventions are not observed. Similarly, not all outcomes may be available in all databases e.g. deaths. Some datasets may not capture COVID-19 diagnoses or tests occurring outside of hospital. Only the cohorts and outcomes that can reliably be identified will be assessed in the analyses. Since the vaccination programs changed over time (e.g. the primary vaccine courses targeted the general population, while the 4th dose were offered to more vulnerable people), the characteristics of patients receiving different doses may differ. However, we will stratify our analysis by prior vaccines whenever the power allows. It will also be assumed that vaccination recording is complete. Due to the availability of more recent data (CPRD is available until July 2022), some databases may have relative short follow-up time for study cohorts, and therefore may impact on the 90-days and 180-days incidence rates. The data elements that each data partner can provide will be detailed. The contextualisation of incidence rates using a historical background period assumes that coding practices and data recording are similar over time. However, this method has been used in previous studies focused on the 1st wave of covid, conducted by the same research group. [20,21] The analysis will calculate crude incidence rates and standardised incidence rates accounting for age and sex only. Differences in other potential confounders factors may exist and the characteristics of each cohort and stratification group will be inspected. No validation of outcomes using case note review will be performed.

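### Section 8.3 sets one study period from 1 December 2021 that cannot fit cohorts 1 and 5; the vaccinated cohort has no calendar entry date, and no stratum separates vaccinations before and during Omicron

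*Protocol*

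**What the plan says.** Protocol section 8.3 defines the study period once, for the whole study: "The study period will start depending upon when the Omicron variant became established in Europe commencing from 1st December 2021". It closes it database by database: "The end of the study period will be the last available date of data collection for each contributing dataset". No cohort is exempted.

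Section 8.5 then treats the cohorts differently. Cohorts 2 and 3 carry the 1 December 2021 date in their own criteria, and cohort 4 inherits it through cohort 3. Cohort 1 is followed from 1 January 2017 to 31 December 2019. Cohort 5 is defined by "a vaccination record identified by brand (with the index date the date of vaccination record") and by "whether the vaccination record is 1st, 2nd, 3rd or 4th dose", with no calendar date. Table 2 gives only the vaccination date as its time anchor, and Table 3 gives its assessment window as n/a.

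The abstract describes the third population as "People vaccinated against SARS-CoV-2 (+/- during the period when OMICRON was the dominant variant"). In section 7, objective 2 is limited to the Omicron period. Objective 3 asks for rates "among patients with SARS-CoV-2 vaccination within 30-, 60-, 90- and 180-days, stratified by prior infection status", without that limit. Objective 5 takes "different SARS-CoV-2 vaccine doses compared to the background population, using incidence rates estimated in objectives 1 to 3".

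The strata in sections 8.8.1, 8.8.2 and 8.8.5 and in Table 8 are age, sex, prior infection, prior vaccination (with brand in Table 8), hospitalisation and immune status. None is a calendar or variant period.

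**The concern.** Cohort entry is a core protocol element, and here two sections give different answers for one of the exposed cohorts. Whoever programs cohort 5 must choose between 8.3 and 8.5, and the abstract does not settle it.

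Each choice has a cost. Applying 8.3 limits the first- and second-dose cohorts to people who started vaccination on or after 1 December 2021, although section 11 says "the primary vaccine courses targeted the general population, while the 4th dose were offered to more vulnerable people". Applying 8.5 lets in doses from the whole programme. Post-vaccination follow-up then spans different circulating variants, in a study whose title sets it in the context of Omicron.

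Variant period can matter for a vaccine rate because section 8.4 does not end follow-up at SARS-CoV-2 infection. Thromboses that follow an infection after vaccination count towards the vaccine rate. Section 6 reports that earlier studies found a much larger excess of venous events after infection than after vaccination, and says that risk with Omicron may differ from earlier variants.

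**Working it through.** The protocol states no figure for cohort 5 by period, so there is nothing to reproduce. The check has four steps.

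**1. Does 8.3 fit each cohort?**
- Cohort 1: no. It ends on 31 December 2019, before the stated start.
- Cohorts 2 to 4: yes.
- Cohort 5: undetermined, as set out above.
- The Estonian Biobank (objective 1 only) has a lock of 31/3/2021, which is 245 days before 1 December 2021. Read literally, 8.3 gives it an empty study period.
- The other date rules do not settle cohort 5. Visibility since 1 January 2020 (abstract) and 365 days of prior data (8.5) concern history, not when a vaccination may be indexed.

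**2. Literal 8.3: how much entry time is left?** Inputs are the data locks in Table 1, read as day/month/year (31/3/2021 allows no other order), and the 180-day maximum follow-up in 8.4. Entry window = lock − 1 December 2021. Index days with full follow-up = window − 180.

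| Database | Lock | Window (days) | Full 180 days possible | Share |
|---|---|---|---|---|
| SIDIAP | 1/6/2022 | 182 | 2 | 1% |
| CPRD GOLD | 07/2022 (1 to 31 July) | 212 to 242 | 32 to 62 | 15% to 26% |
| IQVIA Germany | 1/9/2022 | 274 | 94 | 34% |
| IPCI | 1/12/2022 | 365 | 185 | 51% |

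Counting both end dates, SIDIAP has 3 such dates (1 to 3 December 2021). These are shares of calendar days, not of vaccinations.

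**3. Literal 8.3: how many vaccinations are lost?** Table 1 lists records by brand. SIDIAP: 1,152,432 + 257,806 + 6,548,545 + 3,371,395 = 11,330,178, or 1.95 per active person (5.8M). None is split by dose or date, so the loss cannot be computed. If s is the share of a dose's records before 1 December 2021 (assumed), the share kept is 1 − s and the confidence interval on the log rate widens by 1/√(1 − s):
- s = 25%: 75% kept, interval × 1.15
- s = 50%: 50% kept, × 1.41
- s = 75%: 25% kept, × 2.00
- s = 90%: 10% kept, × 3.16
- s = 95%: 5% kept, × 4.47

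**4. Unrestricted entry: how far can a pooled rate drift?** Let r be the rate before Omicron divided by the rate during Omicron, with equal person-time per record. Pooled rate / Omicron-only rate = s·r + (1 − s). Both s and r are assumed, with r from 0.5 to 2:
- s = 50%: 0.5 × 0.5 + 0.5 = 0.75, up to 0.5 × 2 + 0.5 = 1.5
- s = 90%: 0.9 × 0.5 + 0.1 = 0.55, up to 0.9 × 2 + 0.1 = 1.9
- r = 1: exactly 1 for any s

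**The case against.** The best defence is that the protocol means cohort 5 to be unrestricted, and that only 8.3 is loosely worded. Objectives 2 and 4 mention the Omicron period and objective 3 does not. The headings of cohorts 2, 3 and 4 mention it and that of cohort 5 does not. The +/- in the abstract reads naturally as with or without. Since 8.3 already fails for cohort 1, it was probably written with the infection cohorts in mind. Pooling periods is then compatible with objective 3 as worded. Section 11 acknowledges that recipients differ by dose, offers stratification by prior vaccines, and admits that short follow-up may affect the 90- and 180-day rates.

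Most of this stands: unrestricted entry is the better-supported reading. It does not remove the contradiction in 8.3, and under that reading no planned stratum separates the periods. Stratifying by prior vaccines separates dose histories, not calendar time.

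The defence also rightly limits what may be inferred:
- A reader might conclude that most first and second doses are lost, or that particular brands suffer most. Table 1 has no dates by dose or brand, so neither can be shown.
- A reader might conclude that a planned vaccine-versus-infection estimate is invalid. None is planned: objective 5 and section 8.8.5 compare each cohort with the pre-pandemic background.
- A reader might fear that databases will build cohort 5 differently. Section 5 lists analytical code to be created and then executed on the data, and nothing indicates that each database sets its own entry window.

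**Conclusion.** The point holds as a contradiction plus a missing split. Section 8.3 is wrong as written for cohort 1, conflicts with cohort 5, and leaves the abstract's +/- unresolved. This needs no assumption.

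The consequence depends on the reading. Under literal 8.3, the 180-day vaccine rates in SIDIAP would rest almost wholly on truncated follow-up (2 of 182 index days complete), and an unknown share of vaccinations would be dropped. Under unrestricted entry, cohort 5 rates and SIRs mix variant periods while the COVID-19 SIRs come only from Omicron. Bias relative to an Omicron-only vaccine rate is plausible but not proven. The 0.55 to 1.9 range rests on an assumed 90% of doses before December 2021 and an assumed twofold rate difference in either direction; if the rates are equal, the pooled rate does not change.

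This should be corrected before the cohorts are built. It is more than wording, because neither reading lets the plan as written report a sound Omicron-period vaccine rate alongside the whole-programme one.

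**What to change.** 1. In 8.3, replace the single period with one entry period per cohort: cohort 1, 2017 to 2019; cohorts 2 to 4, from 1 December 2021; cohort 5, from the first COVID-19 vaccine record in each database to its lock. Carry the cohort 5 dates into section 8.5 and Tables 2 and 3.
2. Replace +/- in the abstract with the matching statement.
3. In 8.8.2, 8.8.5 and Table 8, report cohort 5 rates and SIRs by dose and brand, split by index date before versus on or after 1 December 2021, where counts allow.
4. State that any side-by-side reading with the Omicron COVID-19 SIRs uses the later stratum.

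Label the earlier stratum by index date rather than as pre-Omicron follow-up. A dose indexed from 4 June to 30 November 2021 has a 180-day window that reaches 1 December 2021 or later (4 June + 180 days = 1 December). Only the later stratum is purely Omicron time, and it remains exposed to the short windows tabulated above.

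The cost is protocol wording and one stratification on a date already held. The downside is smaller strata: some brand-by-dose cells will be too sparse to report.

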8.4 Follow-up

For cohort 1, follow-up will begin on January 1st 2017 and continue up until the first of: outcome of interest, loss to follow-up, death or December 31st 2019. For cohorts 2 to 5, follow-up will begin on their index date and continue up until the first of: outcome of interest, end of observation period, end of data availability, death, or either 30-, 60-, 90- or 180-days after the index date (depending upon the follow-up time period of interest).

Table 2: Operational Definition of Time 0 (index date) and other primary time anchors

Study population name(s)	Time Anchor Description (e.g. time 0)	Number of entries	Type of entry	Washout window	Care Setting ¹	Code Type	Diagnosis position	Incident with respect to...	Measurement characteristics / validation	Source of algorithm
Background population (cohort 1*)	January 1 st 2017 or after when they have 365 days of prior history	Multiple	General population	n/a	n/a	n/a	n/a	n/a	n/a	n/a
SARS-CoV-2 infection cohort (cohort 2*)	Date of test for the positive test result for SARS-CoV-2, or date of clinical diagnosis of COVID-19	Multiple	incident	No covid-19 infection within 3 months prior	OP	SNOMED codes (see appendix)				
hospitalised with COVID-19 cohort (cohort 3*)	Date the date of hospital admission	Multiple	incident	No hospitalization within	IP	SNOMED codes (see appendix)				

This document represents the views of the DARWIN EU® Coordination Centre only and cannot be interpreted as reflecting those of the European Medicines Agency or the European Medicines Regulatory Network.

	Phase II C3-001 – Study Protocol	
	Author(s): [name], [name]	Version: v3.1
	Dissemination level: public	

				3 month s prior						
Intensive care service cohort (cohort 4*)	Date of the following depends on availability in data, descend priority: 1.)Date of intensive care service (mechanical ventilation, tracheostomy, or extracorporeal membrane oxygenation (ECMO)); 2.)Date of ICU admission; 3.)Date of hospital admission.	Multiple	incident	n/a	IP	SNOMED (see appendix)	n/a	Covid-19 hospitalized	n/a	n/a
Vaccinated cohort (cohort 5*)	date of vaccination record	Multiple	n/a	21 days	OP	RxNorm codes (see appendix)				

*Cohorts number as described in 8.5 study population with inclusion and exclusion criteria.

¹ IP = inpatient, OP = outpatient, ED = emergency department, OT = other, n/a = not applicable

Description of the different items from the table can be found below:

Study population name(s): A brief text descriptor naming the study population that is identified for a primary or secondary analysis (e.g. exposed, comparator, pregnant women, patients with diabetes)

Time anchor description: A brief text description of the criterion used to define the time anchor, including at least one entry to define time 0, the point at which the patient enters the cohort (e.g. date of incident dispensation of Drug X, date of heart failure diagnosis, last menstrual period)

Number of entries: Indicate whether patients are allowed to enter the study population only once or multiple times (e.g. single entry, multiple entry)

Type of entry: Indicate whether the criterion for entry to the study population reflects an incident, prevalent, or other condition.

	Phase II C3-001 – Study Protocol	
	Author(s): [name], [name]	Version: v3.1
		Dissemination level: public

Washout window: If entry to the study population is defined as incident, use bracketed numbers representing time intervals anchored on a primary anchor (usually time 0) to specify the washout window. For example, [-180, -1] would reflect a washout window of 180 days prior to time 0, where the brackets indicate that the window is inclusive of the endpoints.

Care setting: Specify the care setting(s) that are used in the algorithm to define the time 0 (or other primary anchor) criterion. For example, IP = inpatient, ED = emergency department, etc.

Code type: Specify the type(s) of clinical codes that are used to define the time 0 (or other primary anchor) criterion.

Diagnosis position: If the algorithm to define the time 0 (or other primary anchor) criterion used inpatient codes, specify whether the algorithm restricts to primary diagnosis codes (indicating that the code is the primary reason for the encounter) or allows codes in secondary or any position (e.g. primary, secondary, any, n/a)

Incident with respect to: If the type of entry is defined as incident, provide a brief text description of what the patient is required to be incident to. For example, when identifying incident users of Drug X (oral formulation only), the investigator may wish to require that patients be incident with respect to Drug X (oral formulation) as well as Drug X (intravenous formulation) and Drug Y. This would be operationalized as having no record of exposure to any of these drugs during the specified washout period.

Measurement characteristics/validation: If there are measurement characteristics for the outcome algorithm (e.g. PPV, sensitivity, specificity) from publications, or from outcome validation within the study population (e.g., medical record review), provide this information.

Source of algorithm: Specify the source of algorithms to define the time 0 or primary anchor criteria.

The table below further describes the operational definitions with regard to the follow-up start and the follow-up end.

Follow up start	Day 1	Index date
Follow up end¹	Select all that apply	Specify
Date of outcome	Yes	
Date of death	Yes	
End of observation in data	Yes	

	Phase II C3-001 – Study Protocol	
	Author(s): [name], [name]	Version: v3.1
	Dissemination level: public	

Day X following index date (specify day)	Yes	180 days after index date
End of study period (specify date)	Yes	End of data availability per database
End of exposure (specify operational details, e.g. stockpiling algorithm, grace period)	n/a	
Date of add to/switch from exposure (specify algorithm)	n/a	
Other date (specify)	n/a	

¹ Follow up ends at the first occurrence of any of the selected criteria that end follow up.

